5.1.1 Treatment plan for Part 1 (Phase 1b)

Dosing levels for Part1 of the study are listed below in **Table 5.1** and dose escalation will proceed as outlined in Figure 5.1. Agents will be dosed daily in a 28-day cycle according to the description outlined in Table 5.2. A 28-day cycle has been used in previous combination studies with trametinib, such as the study combining trametinib and dabrafenib, summarized in section 2.2.1.4. Subjects will be assessed for toxicities and safety at weekly intervals during the first 28day cycle, at two week intervals during cycle two, and monthly thereafter. Subjects will undergo radiographic assessments of tumor response every 2 cycles (8 weeks +/- 1 week). The schema for dose escalation is shown below in **Table 5.3**, utilizing standard Phase 1 cohorts of 3 subjects per dose level. The occurrence of 1 dose limiting toxicity (DLT; defined in Section 5.2) will prompt expansion of a given dose level to 6 subjects. The occurrence of 2 DLTs in a given dose level will indicate that the maximal tolerated dose (MTD) has been exceeded, and expansion of the prior dose level to 6 subjects will occur, if not already performed. Patients will be replaced if they are not evaluable for the DLT window. The dose of each agent to be used for Part 2 (Phase 2) of the study (the recommended Phase 2 dose (RP2D)) will be the highest dose level at which no more than 1 subject out of 6 experiences a DLT. Dose escalation will proceed until the MTD/RP2D have been determined, or until the RP2D of each compound individually (2mg daily for trametinib; 325mg daily for navitoclax) is reached (represented by dose level 7). If the MTD is reached before dose level 7, alternative dosing schemes will be considered by the investigators in which trametinib is dosed intermittently in an effort to reduce toxicity (denoted as Schedule C). If necessary, the exact details of these alternative dosing schemes will be designed at a future date through a protocol amendment.

[figure not shown]
Table 5.1: Dosing Levels for Part 1 (Phase 1b)

	Dose Escalation Levels	3
]	Dose
Dose Level	Trametinib	Navitoclax
	(mg) PO daily	(mg) PO daily
Level 1	1	150

Level 2	1.5	150
Level 3*	1.5	200
Level 4*	2	200
Level 5*	2	250
Level 6*	2	300
Level 7*	2	325

^{*}Dose levels 3-7 will include a 7-day lead-in dosing period for navitoclax at 150 mg PO daily.

Figure 5.1: Dose Escalation Schema for Part 1 (Phase1b)

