Dose levels 1-3 will be enrolled according to Schedule A (i.e. dosing cohorts 1A, 2A, 3A). After completion of dose level 3A, if dose escalation is warranted per the criteria outlined in Table 5.3 above, an investigator meeting will be held with NCI/CTEP and pharmaceutical collaborators to review safety data. Pharmacokinetic data will be reviewed to evaluate for any evidence of drug interaction, and adverse event data will be reviewed to evaluate for any potentiation of toxicity (in particular, thrombocytopenia) by the combination. If significant safety concerns are noted, dose escalation will proceed for the remainder of the study according to Schedule A (i.e. to dosing cohort 4A, 5A, 6A, 7A). If no significant safety concerns are noted, and it is deemed safe to proceed, dosing will return to dose level 1 according to schedule B (i.e. dosing cohort 1B). Dose escalation will then proceed according to Schedule B to dosing cohort 3B. Since both dose levels 2 and 3 involve beginning with 150 mg navitoclax and 1.5 mg trametinib, it is not necessary to evaluate dose levels 2 and 3 both according to schedule B, as both would test the safety of initiating navitoclax and trametinib simultaneously at these same doses. Therefore, dose escalation will proceed directly from cohort 1B to cohort 3B. If >1 DLT is experienced within dosing cohort 1B or within 3B, then Schedule B will be abandoned, and dose escalation will proceed with dosing cohort 4A. If dosing cohort 3B is completed with ≤1 DLT, then a second investigator meeting will be held with NCI/CTEP and pharmaceutical collaborators to review safety data. Pharmacokinetic data will be reviewed to evaluate for any evidence of drug interaction, and adverse event data will be reviewed to evaluate for any potentiation of toxicity (in particular, thrombocytopenia) by the combination. If the investigators and NCI/CTEP and pharmaceutical collaborators agree that Schedule B demonstrates a comparable or improved safety profile relative to Schedule A, then dose escalation will proceed according to Schedule B (i.e. to dosing cohort 4B, 5B, 6B, 7B) until the RP2D is determined. However, if evidence of drug interaction exists, or if the investigators and NCI/CTEP and pharmaceutical collaborators agree that Schedule A demonstrates a superior safety profile, particularly as it relates to navitoclax-associated thrombocytopenia, then dosing will proceed for the remainder of the study according to Schedule A (i.e. to dosing cohort 4A, 5A, 6A, 7A) until the RP2D is determined. If, however, unacceptable toxicity (either >1 DLT or toxicity not meeting criteria for DLT, but deemed to be unacceptable by investigators) is observed at a given dose level independent of schedule A or B, then and alternative dosing schedule (Schedule C) will be explored with intermittent trametinib dosing (days 1-14 only of each 28 day cycle), beginning at the last dose level completed. With Protocol Version 10 (dated 8/9/16), there will be no further Dose Escalation on Schedule A or B.

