5.2 Definition of Dose-Limiting Toxicity

Dose-limiting toxicity (DLT) is based on the CTEP Active Version 4 of the NCI Common Terminology Criteria for Adverse Events (CTCAE). CTCAE v5.0 will be utilized beginning April 1, 2018. DLT refers to toxicities experienced during the first 42 days of treatment. A DLT will be defined as follows:

Any grade 4 toxicity

Version Date: July 22, 2022

- Grade 3 fatigue, persistent for more than 7 days
- Grade ≥ 3 nausea, diarrhea, or vomiting despite maximum supportive care and persisting more than 72 hours
- Grade \geq 3 neutropenia with fever > 38.5°C
- Grade 3 thrombocytopenia with clinically significant bleeding. Clinically significant bleeding will be defined as any bleeding requiring transfusion, hospitalization, or medical or surgical intervention. Clinically significant bleeding will only be considered a DLT if it is associated and attributable to study drug induced thrombocytopenia.
- Ejection fraction < lower limit of normal (LLN) with an absolute decrease of >10% from baseline with confirming assessment within 7 days.

Management and dose modifications associated with the above adverse events are outlined in Section 6.

Dose escalation will proceed within each cohort according to the scheme shown in **Table 5.3** above. Dose-limiting toxicity (DLT) is defined above.

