6.1.7 Trametinib Dose Modification for Reduced Left Ventricular Ejection Fraction

Decreases of the left ventricular ejection fraction (LVEF) have been observed in patients receiving trametinib. Therefore, ECHOs or MUGAs must be performed in regular intervals outlined in the Study Calendar. The same procedure (either ECHO or MUGA, although ECHO is preferred) should be performed at baseline and at follow-up visit(s).

Trametinib Dose Modification Guidelines and Stopping Criteria for LVEF Decrease		
Clinic	LVEF-drop (%) or CTCAE grade	Action and Dose Modification
Asymptomatic	Absolute decrease of >10% in LVEF compared to baseline and ejection fraction below the institution's LLN.	 Interrupt trametinib and repeat ECHO within 2 weeks.^a If the LVEF recovers within 4 weeks (defined as LVEF ≥LLN and absolute decrease ≤10% compared to baseline): Consult with the CTEP trametinib medical monitor and request approval for restart. Restart treatment with trametinib at reduced dose by one dose level.^b Repeat ECHO 2, 4, 8 and 12 weeks after re-start; continue in intervals of 12 weeks thereafter. If LVEF does not recover within 4 weeks: Consult with cardiologist. Permanently discontinue trametinib. Report as SAE Repeat ECHO after 2, 4, 8, 12, and 16 weeks or until resolution. Consult with the CTEP medical monitor.^d
Symptomatic	 Grade 3: resting LVEF 39-20% or >20% absolute reduction from baseline Grade 4: Resting LVEF ≤20%. 	 Permanently discontinue trametinib. Report as SAE. Consult with cardiologist. Repeat ECHO after 2, 4, 8, 12, and 16 weeks or until resolution.

^a If ECHO does not show LVEF recovery after 2 weeks, repeat ECHO 2 weeks later.

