13.5 Reporting and Exclusions

13.5.1 Evaluation of Toxicity

All patients will be evaluable for toxicity from the time of their first treatment with navitoclax and/or trametinib.

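### Section 5.2 requires an LVEF-fall DLT to be confirmed within 7 days, but 6.1.7 lets the repeat ECHO wait 2 weeks, so DLT status can depend on when the repeat is booked

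*Combined protocol and SAP*

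**What the plan says.** Section 5.2 sets a DLT period of the first 42 days of treatment. Its cardiac item is an ejection fraction below LLN with an absolute fall of more than 10% from baseline, "with confirming assessment within 7 days". The section then sends the reader to Section 6 for management of the listed events. Any grade 4 toxicity is separately a DLT.

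The asymptomatic row of 6.1.7 has the same trigger: "Absolute decrease of >10% in LVEF compared to baseline and ejection fraction below" the institution's LLN. The action is "Interrupt trametinib and repeat ECHO within 2 weeks", with a further ECHO 2 weeks later if there is no recovery. The table makes no exception for Part 1 or for the DLT period.

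On who is counted, Section 5.1.1 says "Patients will be replaced if they are not evaluable for the DLT window", without defining that term. Section 13.5.1 says only "All patients will be evaluable for toxicity from the time of their first treatment" with either drug. Section 5.1.1 also records that from Protocol Version 10 "there will be no further Dose Escalation on Schedule A or B". It keeps Schedule C, which gives trametinib on days 1-14 of each 28-day cycle. The Part 1 Schedule C calendar in Section 10 has one scheduled on-treatment ECHO or MUGA in the DLT period, at C1D28 with a window of D23-D29.

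**The concern.** A site that meets the threshold in Part 1 and manages it by the section to which 5.2 refers can book the repeat on day 10 and comply with 6.1.7. If that repeat shows the fall persisting, the event is real but was not confirmed within 7 days, so on its wording 5.2 does not count it. If the repeat shows recovery, a day-7 repeat might still have confirmed the fall, because trametinib is held in between. In both cases the appointment date, and not only the patient's cardiac function, decides the DLT status.

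Cohorts have 3 to 6 patients, so one reclassified patient matters. Under Table 5.3, 1 of 3 (expand to 6) can become 0 of 3 (escalate), and 2 of 6 (stop) can become 1 of 6. The same count fixes the recommended phase 2 dose.

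**Working it through.** **1. The two windows.** Confirmation under 5.2 covers days 0-7 after the fall; the repeat under 6.1.7 covers days 0-14. Days 8-14 are allowed by 6.1.7 and fall outside 5.2. For a fall found at the C1D28 ECHO, confirmation is due by day 28 + 7 = 35, while 6.1.7 allows the repeat until day 28 + 14 = 42. That gap, days 36-42, lies inside the 42-day DLT period.

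**2. Timing under Schedule C.** The last cycle 1 trametinib dose is on D14.

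- ECHO on D23-D29: 23 - 14 = 9 to 29 - 14 = 15 days after that dose.
- Repeat 8-14 days later, cycle 2 trametinib held: 9 + 8 = 17 to 15 + 14 = 29 days after that dose.

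With the effective half-life of about 4.5 days in Section 2.2.1.2, this is 2.0-3.3 half-lives at detection and 3.8-6.4 at a late repeat. Section 6.1.7 itself provides for recovery within 4 weeks of interruption. Section 2.2.1.3 reports that cardiomyopathy resolved in 10 of 14 patients. A later repeat is therefore more likely to show recovery.

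**3. The plan's escalation table.** For a true DLT rate p, the rule in Table 5.3 gives

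E(p) = (1 - p)^3 + 3p(1 - p)^2 × (1 - p)^3 = (1 - p)^3 + 3p(1 - p)^5.

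At p = 10%, 20%, 30%, 40%, 50% and 60% this is 90.6%, 70.9%, 49.4%, 30.9%, 17.2% and 8.2%. Section 13.1.1 states 91%, 71%, 49%, 31%, 17% and 8%, so the table is reproduced.

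**4. Illustrative size.** The documents give no rate of late repeats and no rate for this exact event. The nearest input is in Section 2.2.1.3: in the phase 3 trametinib monotherapy trial, 14 of 211 patients had cardiomyopathy, five of them within the first month, so 5/211 = 2.37%. Assume that none, half or all of these would be re-imaged after day 7 and left uncounted. The uncounted rate m is then 0, 2.5/211 = 1.18% or 2.37%, and the chance of escalating is E(p - m).

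| True DLT rate | None late | Half late | All late |
|---|---|---|---|
| 20% | 70.9% | 73.4% | 75.9% |
| 30% | 49.4% | 51.9% | 54.4% |

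Worked example at 20%, all late: p - m = 0.1763, and E = 0.8237^3 + 3 × 0.1763 × 0.8237^5 = 0.559 + 0.201 = 0.759. The rise is about 5 points at either rate if all repeats are late, and about 2.5 points if half are.

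**The case against.** The strongest reply is that nothing conflicts. Seven days lies inside two weeks, 5.2 sets its own confirmation interval and delegates only management, and a Part 1 site bound by both sections should re-image by day 7. That is right as far as it goes, and a reader who infers a contradiction goes too far. What remains is that the table a site works from names only the longer limit.

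A reader might also infer that a fall re-imaged on days 8-14 has no DLT status at all. The documents do not support this. Confirmation within 7 days is part of the definition, so the literal result is not a DLT unless grade 4. A reader might further infer that such a patient would be replaced. Nothing links a late ECHO to non-evaluability for the DLT window, so no size is attached to that reading here.

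The input in step 4 fits loosely. It includes cardiac failure and does not require the 5.2 threshold or confirmation. It also comes from continuous 2 mg dosing, which is more trametinib than Schedule C gives. In the other direction, the 42-day period is longer than one month. The full 14/211 would be too large an input, because onset in that trial ran to day 156.

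Other controls also limit the harm. Trametinib is interrupted, and restart needs medical monitor approval and a reduced dose. Non-recovery within 4 weeks means permanent discontinuation and SAE reporting. Section 5.1.1 allows a move to Schedule C for "toxicity not meeting criteria for DLT, but deemed to be unacceptable by investigators". These protect the patient and keep the event visible, but none of them sets the DLT count.

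**Conclusion.** The point holds as a minor mismatch in timing. A repeat that complies with 6.1.7 can fall too late for 5.2, and a persistent fall below grade 4 then drops out of the count that drives Table 5.3. The size is at most about 5 points on the escalation probability at true DLT rates of 20% and 30%. That assumes a 2.4% event rate and every repeat late; the effect is zero if sites re-image by day 7.

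It does not bear on Part 2, which has no DLT-based escalation. Escalation on Schedules A and B is closed. The documents do not say whether Schedule C escalation is still open, so the practical benefit may be limited to classifying such events clearly when the basis for the phase 2 dose is reported.

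**What to change.** In 6.1.7, for Part 1 patients in the 42-day DLT period, require the repeat ECHO or MUGA within 7 days of any fall that meets the 5.2 threshold, with a cross-reference to 5.2. Keep the existing follow-up series. Word it for any such fall, because the symptomatic row's listed series also starts at 2 weeks.

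Do not align the sections by widening 5.2 to 14 days: trametinib is held meanwhile, and a later repeat is more likely to show recovery.

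The cost is a short wording change, an earlier booking for an ECHO that is already required, and occasionally one more ECHO to document recovery.

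How to score a fall whose repeat is still late or missing is for the investigators and CTEP to decide. Counting it automatically as a DLT would reverse the confirmation requirement in 5.2, and one unconfirmed reading could then expand a cohort or stop escalation at a tolerable dose. That rule is a trade-off and not part of the required change.

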5.3 General Concomitant Medication and Supportive Care Guidelines

5.3.1 Trametinib

Because there is a low potential for interaction of trametinib with other concomitantly administered drugs through the cytochrome P450 system, the case report form must capture the concurrent use of all other drugs, over-the-counter medications, or alternative therapies. The Principal Investigator should be alerted if the patient is taking any agent known to affect or with the potential to affect selected CYP450 isoenzymes.

5.3.2 Navitoclax

Potential issues with navitoclax include drug-drug interactions and thrombocytopenia. See the navitoclax supportive care guidelines (Section 6) currently included in all company-sponsored protocols for managing thrombocytopenia (with platelet transfusion recommendations), lymphopenia, and tumor lysis syndrome.

In adult monotherapy clinical studies, reductions in circulating platelet counts were observed in an expected, dose-dependent predictable manner, with the nadir occurring 3-5 days after the first dose of navitoclax followed by a subsequent recovery during ongoing dosing. This effect is reversible with interruption of study drug. Platelets recover towards baseline with continued dosing, but may not necessarily reach baseline levels. **Therefore, adequate platelet monitoring should be obtained, including after initiation of navitoclax therapy and when platelet counts are noted to be <50,000/mm³ (see also Section 6.2).** Attenuated lead-in dosing appears to ameliorate the risk of early grade 4 thrombocytopenia, and continuous dosing

mitigates major swings in circulating platelet counts.

Colony stimulating factors (G-CSF, GM-CSF) or human erythropoietin will be considered during administration of navitoclax if deemed necessary by the investigator.

The following concomitant medications are not allowed during navitoclax administration due to mechanistic-based platelet toxicities from navitoclax: Warfarin, Clopidogrel (Plavix), ibuprofen, tirofiban (Aggrastat), and other anticoagulants, drugs, or herbal supplements that affect platelet function. Administration of heparin to keep subject's infusion lines patent is allowed. Low-dose anticoagulation medications that are used to maintain the patency of a central intravenous catheter are allowed.

Aspirin will not be allowed within 7 days prior to the first dose of navitoclax or during navitoclax administration. However, subjects who have previously received aspirin therapy for thrombosis prevention, may resume a low dose (*i.e.*, maximum 100 mg QD) of aspirin if platelet counts are stable (≥50,000/mm³) through 6 weeks of navitoclax administration. All decisions regarding treatment with aspirin therapy will be determined by the investigator in conjunction with the medical monitor.

Disulfiram is not allowed due to potential drug interactions.

Navitoclax is a moderate inhibitor of the activity of cytochrome P450 (CYP) isoenzyme CYP2C8 (IC₅₀ = 3.4 μ M or 3.3 μ g/mL) and is a potent inhibitor of CYP2C9 activity (IC₅₀ = 1.0 μ M or 0.97 μ g/mL). At the expected biologically effective plasma concentration of about 3 to 5 μ M (3–5 μ g/mL), navitoclax is likely to inhibit the metabolism of drugs that are substrates for CYP2C8 and CYP2C9. Clinically relevant CYP2C8 substrates include paclitaxel, statins, and glitazones, whereas phenytoin and warfarin are substrates of CYP2C9. Co-dosing with CYP2C8 and CYP2C9 substrates should be undertaken with caution.

Navitoclax is metabolized in the liver by CYP3A4. Strong CYP3A4 inducers/inhibitors are NOT allowed. Weak or moderate inhibitors/inducers are allowed, but should be used with caution. CYP3A4 inhibitors such as ketoconazole and clarithromycin are not allowed 7 days prior to the first dose of navitoclax or during navitoclax administration.

5.4 **Duration of Therapy**

In the absence of treatment delays due to adverse event(s), treatment may continue until one of the following criteria applies:

- Disease progression,
- Intercurrent illness that prevents further administration of treatment,

- Unacceptable adverse event(s),
- Patient decides to withdraw from the study, or
- General or specific changes in the patient's condition render the patient unacceptable for further treatment in the judgment of the investigator.
- The study reaches its planned stopping date, which will be 2 years after the last patient's first dose of study drugs. However, in the event that a patient or patients have an excellent response to therapy that is ongoing at the time of this planned stopping date, the possibility of continuing treatment for the patient(s) in question will be subject to discussion.

5.5 **Duration of Follow Up**

Patients will be followed until the resolution or stabilization of all study-related toxicity and for a minimum of 30 days after removal from study or until death, whichever occurs first. Patients removed from study for unacceptable adverse event(s) will be followed until resolution or stabilization of the adverse event.

5.6 Criteria for Removal from Study

Patients will be removed from study when any of the criteria listed in Section 5.4 applies. The reason for study removal and the date the patient was removed must be documented in the Case Report Form.

6. DOSING DELAYS/DOSE MODIFICATIONS

When a situation arises that requires dose interruption or discontinuation of one of the study drugs based on the criteria outlined below, the other study drug should be continued as indicated according to the protocol until the patient meets criteria for removal from study as outlined in Section 5.4.

6.1 Trametinib Dose Modifications

The table below outlines the dose levels to be used for any necessary trametinib dose modifications:

Dose Level	Trametinib Dose/Schedule
0	2 mg QD
-1	1.5 mg QD

Version Date: July 22, 2022

-2	1 mg QD
-3	0.5 mg QD

A maximum of two trametinib dose level reductions are allowed. If a third dose level reduction is required, treatment will be permanently discontinued.

6.1.1 Trametinib Dose Modification for Toxicities Not Specified in Subsequent Sections

Trametinib Treatment Modification for Clinically Significant Toxicities Likely to be Related to Trametinib in the judgment of investigator (This section is not for specific AEs such as hypertension, rash, ejection fraction changes, pneumonitis, diarrhea, liver chemistry, QTc prolongation, or visual changes. Refer to other sections for these specific AEs).		
CTCAE v4 Grade *	Management Guideline	Dose Modification
Grade 1 Grade 2 (tolerable)	Monitor as clinically indicated. Provide supportive care according to institutional	Continue trametinib at current dose level. • Interrupt treatment until resolution to grade 1 or baseline. • Upon resolution, restart treatment at current dose level.
Grade 2 (intolerable) and Grade 3	- standards	 Interrupt treatment until resolution to grade 1 or baseline. Upon resolution to baseline or grade 1, restart with one level of dose reduction If the Grade 3 toxicity recurs, interrupt trametinib; When toxicity resolves to Grade 1 or baseline, restart trametinib reduced by another dose level
Grade 4		Permanently discontinue trametinib.

Trametinib should be discontinued if treatment delay is ≥21 days due to toxicities. If the investigator concludes that continued trametinib will benefit a patient, the study chair and CTEP Medical Monitor may be consulted for the possibility of resuming trametinib, provided that toxicities have resolved to baseline or grade 1.

